12.2.3.1. Primary Endpoint

The primary endpoint is the proportion of participants with protocol-defined SOSE. SOSE is assessed by significant retinal changes from baseline using SD-OCT and qFAF. The details of significant protocol defined retinal changes using SD-OCT and qFAF are defined [Table 5](#).

A detailed list of SD-OCT and qFAF parameters assessed in this study is presented in [Appendix 1](#) and [Appendix 2](#). Clinically significant changes for quantitative measures will be defined as a change from baseline by a threshold taken from previously published coefficient of repeatability ([Table 5](#)). For qualitative assessments, new findings or worsening of findings from baseline exams regarded to be of clinical importance by the Blinded Reading Site will be considered a change from baseline. If either of the automated reading (CST or TMV) is missing or deemed unreliable by the Blinded Reading Site; the parafoveal (inner ring of the ETDRS grid; the annular zone between foveal centered 1 mm diameter circle and 3 mm diameter circle) retinal thickness will be used to impute the missing data.

A descriptive summary table will be produced showing the results by each eye and across both eyes, for each assessment (including follow-up). The actual SD-OCT image of each eye will be included in the eCRF. Data from repeated tests carried out due to abnormal values will not be tabulated. All data, including those from repeat tests, will be provided in a listing.

For this primary endpoint, a participant will be considered to have a clinically significant SOSE if any of the five parameters listed below indicates a change from baseline in either eye at any time point during treatment. The 95% CI of SOSE rate will be calculated by treatment group, using the Clopper Pearson Exact methodology for the proportion of participants who did experience a clinically significant deterioration. The risk difference of the SOSE rates between tafenoquine and placebo will be estimated. The upper limit of two-sided 95% CI for the risk difference will be compared against the protocol pre-specified NI margin.

Table 5: Primary Endpoint Evaluation Criteria

Parameter	Result (change from baseline)	Criteria for Clinically Significant Change from Baseline ^a
SD-OCT CST ^b	Yes/No	Yes = change from baseline of at least 40 μm (15% change)
SD-OCT TMV ^c	Yes/No	Yes = change of $\geq 10\%$ (0.86 mm^3) from baseline
SD-OCT parafoveal (inner ring of ETDRS grid) retinal thickness	Yes/No	Yes = change from baseline of at least 10 μm
SD-OCT ellipsoid and interdigitating zone disruption	Yes/No	Manual reading; Yes = any ellipsoid or interdigitating zone disruption (within the ETDRS grid) Graded as: Foveal (central subfield) Parafoveal (inner or outer ring) Extra macular (none in grid)
Abnormal quantitative auto fluorescence (qFAF) patterns	Yes/No	Manual reading; Yes = change in mid-ring qFAF ₈ unit from baseline of at least 12%

^a Note that these evaluations will be performed by the local site principal ophthalmologist.

^b CST=central subfield thickness

^c TMV=total macular volume

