The primary endpoint for the safety of tafenoquine versus placebo is measured by SOSE rate, as assessed by SD-OCT and qFAF parameters. A detailed list of SD-OCT and qFAF parameters assessed in this study is presented in [Appendix 1](#) and [Appendix 2](#). Clinically significant changes for quantitative measures will be defined as a change from baseline by a threshold taken from previously published coefficient of repeatability ([Table 5](#)). For qualitative assessments, new findings or worsening of findings from baseline exams regarded to be of clinical importance will be considered a change from baseline. If either of the automated reading (CST or TMV) is missing or deemed unreliable; the pericentral (inner ring) retinal thickness will be used to impute the missing data.

Descriptive summary tables will be produced showing the results by each eye and across both eyes, for each assessment (including follow-up). Data from repeated tests carried out due to abnormal values will not be tabulated. All data, including those from repeat tests, will be provided in a listing.

For this primary endpoint, a participant will be considered to have a clinically significant SOSE if any of the five parameters listed in [Table 5](#) indicates a change from baseline in either eye at any time point during treatment. The 95% confidence intervals (CI) of SOSE rate will be calculated by treatment group, using the Clopper Pearson Exact methodology for the proportion of

participants who did experience a clinically significant deterioration. The risk difference of the SOSE rates between tafenoquine and placebo will be estimated. The upper limit of two-sided 95% CI for the risk difference will be compared against the protocol pre-specified NI margin.

Secondary Endpoint Measures

- The incidence, severity and relationship to the IMP of AEs will be summarized at $\geq 1\%$ (common) and $\geq 10\%$ (very common) level. Safety laboratory parameters and vital signs up to and including the EOS visit (Week 64) will be summarized descriptively.

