12.2. Analysis and Presentation of Data

12.2.1. General

Detailed aspects of the analysis will be presented in the SAP which will be finalized prior to unblinding.

In general, for safety analyses, descriptive statistics will be tabulated by treatment group for all participants. Unless otherwise stated, all safety analyses will use the Safety Analysis population. The analysis of AEs will consider only treatment emergent AEs (TEAEs), events occurring for the first time, or worsening, during or after the first administration of IMP. The analysis will focus on participant incidence, although for TEAEs of special interest, the number of events will also be provided (i.e., ophthalmic assessments). Tables summarizing TEAEs will be displayed by preferred term and SOC. Analysis of SAEs and the categorization of AEs by severity and relationship to IMP will also be included. AEs leading to study withdrawal or deaths on-study will also be analyzed in tables and/or listings.

Treatment-emergent changes in vital signs and laboratory parameters will be presented using tabulations by group. Descriptive statistics for each parameter and/or the change from baseline at each time point will be provided. Shift tables for selected laboratory endpoints will be presented (ALT, AST, total bilirubin, hemoglobin and methemoglobin) as defined in the SAP. For endpoints measured on a categorical scale the number of participants and proportions will be provided.

Missing data will not be imputed in general, unless otherwise specified. This is a safety study, thus multiplicity adjustment related to the primary and secondary safety endpoints analyses will not be considered.

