APPENDIX 1. SD-OCT FINDING

OCT CST – automated segmentation performed by the Heidelberg Spectralis OCT device will generate an average thickness of the retina in the central 1 mm zone, measured from top of the Internal Limiting Membrane (ILM) to bottom of the RPE (in μm).

OCT TMV – automated segmentation performed by the Heidelberg Spectralis OCT device will generate an average thickness of the retina in the central 6 mm zone, from the top of ILM to the bottom of RPE which provides a volume measurement of the central 6 mm zone (in cubic millimeters).

OCT Parafoveal (inner ring) and perifoveal (outer ring) Retinal Thickness – automated segmentation performed by the Heidelberg Spectralis OCT device will generate an average thickness of the retina in a rim region between the central 1 mm and 3 mm diameter rings and 3 and 6 mm diameter rings, measured from top of the ILM to bottom of the RPE (in μm).

OCT Subretinal Fluid Thickness – manual measure of greatest linear height of any sub retinal fluid (if present) (in μm).

***En face* OCT ellipsoid zone disruption** – manual measurement of the greatest linear extent of ellipsoid layer loss due to foveal photoreceptor damage based on en face OCT scans segmented to the level of ellipsoid zone. Results will be reported as normal or abnormal.

***En face* OCT retinal pigment epithelium layer disruption** – manual measurement of the greatest linear extent of loss of RPE layer due to drug toxicity based on en face OCT scans segmented to the level of RPE layer. Results will be reported as normal or abnormal.

***En face* OCT interdigitation zone disruption** – manual measurement of the greatest linear extent of preserved interdigitating layer due to perifoveal photoreceptor damage based on en face OCT scans segmented to the level of interdigitating layer. Results will be reported as normal or abnormal.

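### A missing CST or TMV is to be imputed from inner-ring thickness, a different region with a different cut-off, and no imputation method is given

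*Combined protocol and SAP*

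**What the plan says.** Section 12.2.1 sets the default: "Missing data will not be imputed in general, unless otherwise specified". Section 12.2.3.1 then makes an exception for two of the primary-endpoint measures. The trigger is "If either of the automated reading (CST or TMV) is missing or deemed unreliable by the Blinded Reading Site", and the remedy is that parafoveal (inner-ring) "retinal thickness will be used to impute the missing data". The synopsis, under Primary Endpoint Measures, repeats the rule with another name for the region: "the pericentral (inner ring) retinal thickness will be used to impute the missing data". Neither place says whether the imputed quantity is the raw value, the change from baseline, the Yes/No result or a model prediction. Neither says which cut-off then applies.

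A participant has a SOSE "if any of the five parameters listed below indicates a change from baseline in either eye at any time point during treatment". Inner-ring thickness is itself one of those five parameters. The synopsis, under Secondary Endpoint Measures, also plans a between-arm difference in the proportion with a clinically significant change for each SD-OCT parameter, defined as in the primary endpoint.

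**The concern.** The donor measure does not match what it is meant to replace. It differs from CST in region, normal level and cut-off, and from TMV in unit as well. It is already counted in its own right, so it brings no independent information to the composite. By Appendix 1 all three measures come from the same device's automated segmentation, so the ring value may also be doubtful when CST or TMV is unreliable. No fallback is given for that case.

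The sentence allows several readings with different results. Some leave the SOSE count alone but alter the CST and TMV components; another can add SOSEs. Two analysts could follow the text faithfully and report different primary-endpoint counts. With an assumed SOSE rate of 1%, about 3 events per arm of 300, a few misclassified participants would matter.

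**Working it through.** **The plan's own figures (Section 12.1).** With 300 per arm, 1% in both arms, margin 2.5 points and one-sided alpha 0.025:
- Standard error = √(2 × 0.01 × 0.99 / 300) = 0.00812. Power = Φ(0.025/0.00812 − 1.960) = Φ(1.117) = 86.8%, against 86% stated.
- For 86% power, n = 293 per arm, against 300 planned.
- P(at least one SOSE in 300) = 1 − 0.99^300 = 95.1%, against 95% stated.

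All three reproduce. None depends on the imputation rule.

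**The three measures (Appendix 1 and Table 5).**

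| Measure | Region | Unit | Cut-off |
|---|---|---|---|
| CST | central 1 mm | µm | "Yes = change from baseline of at least 40" µm (15%) |
| TMV | central 6 mm | mm³: "which provides a volume measurement of the central 6 mm zone (in cubic millimeters") | 10% (0.86 mm³) |
| Inner ring | 1–3 mm annulus | µm | "change from baseline of at least 10" µm |

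**Reading A: copy the ring's Yes/No.** If the ring is Yes, the participant already has a SOSE; if it is No, nothing is added. SOSE cannot change. The CST or TMV component, however, is now judged by a 10 µm rule. For CST that is 10/40, one quarter of its own cut-off.

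**Reading B: copy the ring's change and apply the CST or TMV cut-off.** A ring change of 40 µm or more is also 10 µm or more. A ring change of 10% is 10 µm or more whenever ring baseline is at least 100 µm. Again no SOSE is added, but the component reports change in another region.

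**Reading C: put the raw ring value in place of a follow-up CST.** Exclusion 3(l) requires a screening CST, and Section 8.1 uses screening ophthalmic data as baseline. The baseline is therefore a true CST, and ring would be compared with centre.
- Implied TMV = 0.86/0.10 = 8.6 mm³. The 6 mm circle has area π × 3² = 28.27 mm², so mean thickness = 8.6/28.27 mm = 304 µm.
- Central level: 40/0.15 = 267 µm from Table 5, or 270 µm from Appendix 4.
- The centre is 1/36 of the area. Mean thickness outside it = (36 × 304.2 − 267)/35 ≈ 305 µm, and also about 305 µm with 270.
- Gap if inner and outer rings are equally thick: about 39 µm (from 267) or 35 µm (from 270), with no true change, against a cut-off of 40 µm.
- The inner ring is 8/36 of the area and the outer ring 27/36. If the inner ring is thicker than the outer by x µm, the gap grows by 27x/35. It reaches 40 µm at x ≈ 1.9 (from 267) or 6.3 (from 270).

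The documents do not give the inner-ring level, so the following is an assumption. For a mean gap of 35–65 µm with SD 10–24 µm, P(gap of 40 µm or more in either direction) = Φ((g − 40)/s) + Φ((−40 − g)/s). This runs from 31% (g = 35, s = 10) to 99% (g = 65, s = 10) of stable eyes.

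**Reading D: put the raw ring value in place of TMV.** This cannot be done without a conversion from µm to mm³, and none is given.

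**What Reading C could do to the composite (illustration only).** Let m be the share of participants with an imputed CST and f the share of those falsely flagged, equal in both arms. The SOSE rate becomes 0.01 + 0.99 × m × f.

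| m | f | SOSE rate | Power |
|---|---|---|---|
| 1% | 50% | 1.5% | 71% |
| 1% | 90% | 1.9% | 61% |
| 2% | 50% | 2.0% | 59% |
| 2% | 90% | 2.8% | 46% |

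Both m and f are assumptions; the documents give neither.

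**The case against.** The case on the other side is that the rule speaks of imputing, not of substituting. A prediction of CST or TMV from ring thickness is neither specified nor excluded; it need not distort the components and would rarely change SOSE. Table 5 works in changes from baseline and the ring has its own baseline, so the change reading is arguably the natural one, and it adds no SOSE. The 35–39 µm gap describes the whole zone outside the centre, not the inner ring, and lies just under the cut-off. Shared segmentation shows that failures may coincide, not that they must. The components are secondary outputs, and detail is deferred to a SAP to be finalised before unblinding.

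Most of this stands, and it limits the claim. A reader might infer that the rule must create false SOSEs. The documents do not support that, because it happens only under raw substitution for CST. A reader might also infer that units differ throughout, but CST and ring thickness are both in µm; only TMV differs. Nor does the text say that a thickness near 300 would be entered as a volume near 8.6.

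What remains is that the sentence names a poorly matched donor with no method. Each way of carrying the ring over directly is either idle for SOSE and harmful to the components, or potentially harmful to SOSE.

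**Conclusion.** The rule should go. Under Readings A and B its effect on the primary endpoint is exactly zero, so it serves no purpose there. It does put ring data into the CST and TMV proportions compared between arms, and Reading A does so at a 10 µm threshold. Under Reading C it compares ring with centre and builds in about 35–39 µm against a 40 µm cut-off. That figure rests on the baselines implied by Table 5, the Appendix 4 midpoint, and equal inner and outer ring thickness. The number of false SOSEs cannot be stated, because neither the share of missing or unreliable readings nor the inner-ring level is in the documents.

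A reader might take the power figures under Reading C as showing that the trial is underpowered. They do not: they are conditional on assumed shares and on one reading. The stated power and sample size are correct as calculated.

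**What to change.** Delete the imputation sentence in Section 12.2.3.1 and in the synopsis, and replace it with four rules:
- A missing or ungradable CST or TMV stays missing for that eye and visit.
- SOSE is classified on the remaining gradable criteria.
- CST and TMV component results use observed data only.
- A visit with no gradable SD-OCT is unobserved for the SD-OCT criteria.

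The number of missing or ungradable readings should be reported by arm and visit.

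If a sensitivity analysis is wanted, apply the same rule for ungradable visits to both arms. Counting them as SOSEs on tafenoquine only would be too extreme to inform. With 3/300 on placebo, the Wald upper limit is 2.05% for 4/300 on tafenoquine and 2.501% for 5/300. Starting from 3/300 in each arm, two tafenoquine participants with an ungradable visit would already fail the margin.

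The cost is one sentence in two places and a short SAP paragraph, settled before unblinding. If the change is treated as one to the endpoint, Section 14.2.2 makes it a substantial amendment needing ethics and HRPO approval. No new data are needed and the sample size does not change. Against Readings A and B, deletion leaves the SOSE count as it was.

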2.1.1.2. Retinal Effects

Retinopathy and night vision decline may also be a manifestation of systemic phospholipidosis. As previously described, selected participants in [Study 033](#) underwent more detailed ophthalmic assessments (phospholipidosis safety subgroup). These included fundoscopy, which was performed at baseline (before tafenoquine dosing) and at 6 month’s post-prophylaxis in 69 participants in the tafenoquine Recommended Regimen group and

17 participants in the mefloquine group. Examiners who performed the fundoscopy were aware of the participants' corneal deposits (if present) and were therefore unblinded in that respect. Fundoscopic examinations revealed abnormalities (e.g., granularity/pigmentation of retinal pigment epithelium [RPE], hard drusen) in 27 of 69 (39.1%) tafenoquine Recommended Regimen participants and in 4 of 17 (23.5%) mefloquine participants at the end of dosing. Vision was not affected in any of these individuals. Among the participants with retinal findings, fundus fluorescein angiograms (FFA) were performed in 15 of the 31 cases and were considered abnormal in 4 of 14 (28.6%) of the tafenoquine Recommended Regimen participants and in 1 of 1 (100%) mefloquine participants. When an expert ophthalmology board was asked to review this data, relevance of the retinal findings (based on fundoscopy and FFA) could not be ascertained because no baseline retinal photography data was available. The ophthalmology board noted that the results observed could reflect normal variability and the participative nature of the examinations. They did not consider that the FFA results provided evidence of a drug effect.

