7.7. Unblinding

Any accidental unblinding should also be reported in writing to the sponsor and LMM. The report should include the reason for the unblinding and the steps taken to ensure that the risks of this happening again in the future are minimized.

Special care should be taken to keep the participants masked when examining study physician notices and documents relating to corneal deposits or when the photographer is taking images of these benign changes since these lesions are indicative of tafenoquine exposure and they have no visual consequences, participants should not be told when these deposits are identified during any study visits.

The PI or designated approved study physician will make the decision to un-blind the identity of the IMP in the event that the study blind needs to be broken to make medical decisions regarding participant treatment. If it is determined that unblinding is necessary to assess AEs or SAEs for expedited reporting, the sponsor may decide to request unblinding of a participant. Site staff or sponsor's designee approved to un-blind the IMP for an individual participant will log into the IWRS to obtain the name of the IMP to which the participant was randomized. The IWRS will automatically notify the un-blinded staff member at the Data Management Site who will notify the sponsor. The sponsor will be notified that an unblinding has occurred if unblinding has been performed by the investigator or designee.

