The Lions Eye Institute in Australia or the Retinal Institutes in the US will provide clinical site training materials, certifications of the readers and will perform the initial evaluation of SD-OCT, qFAF and color photos for both eyes. Color photos of the cornea and retina will be used as complementary images. The evaluations performed at these sites will be used for initial reporting of ophthalmologic AEs and SOSEs.

The University of Wisconsin School of Medicine and Public Health, Fundus Photograph Reading Center will perform a masked (the site's evaluation will not be provided) evaluation of SD-OCT, qFAF and color photos for both eyes. Prior to the start of the clinical trial, they will provide training of operators in the form of written instructions for acquiring digital images for SD-OCT, qFAF and color images permit uploading digital images into their EXCELSIOR™ data management platform as well as certification of the readers and the equipment prior to transfer of images to the Fundus Photograph Reading Center for evaluation. They will evaluate SD-OCT and qFAF scans for qualitative and quantitative assessment per protocol-defined outcomes. Color photos will be used as complementary images. On a monthly basis, they will perform data transfer to Fast-Track for inclusion in the main study database. In addition, they will maintain HIPAA and 21 Code of Federal Regulations (CFR) Part 11 compliant computer services with a technical support help desk for users uploading images to the EXCELSIOR™ data management platform.

After data transfer, results from the clinical sites will be compared with that at the Fundus Reading Center by the data management center and the results of the comparison will be provided to the site PI for review.

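### The protocol names two different readers for the primary SOSE endpoint and no rule for which reading is analysed; one of them, the local ophthalmologist, is not shielded from corneal deposits

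*Combined protocol and SAP*

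**What the plan says.** Three places in the combined protocol and SAP assign the reading of the primary endpoint.

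- **Table 5, footnote a (Section 12.2.3.1).** "Note that these evaluations will be performed by the local site principal ophthalmologist". The footnote mark sits on the heading of the criteria column, so it covers all five components.
- **Text of Section 12.2.3.1, above the table.** New or worsened qualitative findings count when "regarded to be of clinical importance by the Blinded Reading Site will be considered a change from baseline". The same body triggers the substitution of parafoveal thickness: "If either of the automated reading (CST or TMV) is missing or deemed unreliable by the Blinded Reading Site".
- **Section 9.2.6.** On the clinical sites: "The evaluations performed at these sites will be used for initial reporting of ophthalmologic AEs and SOSEs". On the Fundus Photograph Reading Center: it "will perform a masked (the site's evaluation will not be provided) evaluation of SD-OCT, qFAF and color photos for both eyes", and "They will evaluate SD-OCT and qFAF scans for qualitative and quantitative assessment per protocol-defined outcomes". The two sets of results are then compared, and the comparison goes to the site PI. No passage says which set is analysed, who settles a disagreement, or whether the PI's review can alter a value.

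On corneal deposits, Section 7.7 says that "these lesions are indicative of tafenoquine exposure", but its precaution is directed at keeping participants masked. Section 8.3 lists slit-lamp deposit grading in the same ophthalmic assessment as SD-OCT and qFAF at Weeks 12, 24 and 52. Section 9.2.6 gives the site colour photographs of cornea and retina as supporting images. Section 2.1.1.2 reports that fundoscopy examiners in Study 033 knew of the deposits and "were therefore unblinded in that respect".

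**The concern.** Two things are at stake.

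First, the source of the primary data is undefined. Where site and centre disagree, either reading can be defended from the text. A choice made after unblinding would be a post hoc choice of the primary result.

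Second, the two readers are not equally protected. A site ophthalmologist who knows that a participant has deposits may suspect the treatment arm, and could then call too many SOSEs on tafenoquine or explain real ones away. The second direction is worse in a safety trial, because it favours a false conclusion of no excess retinal harm. At the planned event rate a handful of calls decides the comparison.

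**Working it through.** **1. The plan's own figures.** Section 12.1 gives a 1% SOSE rate in both arms, a margin of 2.5 percentage points, one-sided alpha 0.025 and 300 per arm.

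- Probability of at least one event in 300 at 1%: 1 − 0.99^300 = 95.1% (stated: 95%).
- Power: Φ(0.025 / √(2 × 0.01 × 0.99 / 300) − 1.96) = Φ(3.077 − 1.960) = 86.8% (stated: 86%).
- Exact enumeration of two binomials with the Wald limit: 85.3%.

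The stated figures reproduce, and the point disputes none of them.

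**2. How many calls matter.** Expected events per arm: 300 × 0.01 = 3. Take 3 placebo SOSEs and compute the upper 95% limit for the risk difference. Wald: d + 1.96 × √(p_T(1 − p_T)/300 + p_P(1 − p_P)/300).

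- 4 against 3: 0.00333 + 1.96 × 0.00877 = 2.05%. Miettinen-Nurminen: 2.499%. Both are below 2.5%.
- 5 against 3: 0.00667 + 1.96 × 0.00936 = 2.501%. Miettinen-Nurminen: 2.96%. Both are above 2.5%.

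So a single call can move the result. Section 12.2.3.1 names an exact method for each arm's rate but none for the risk difference, so both limits are shown; Wald is the one close to the stated 86%.

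**3. Sensitivity to biased reading.** The documents give no misreading rate, so the rates below are assumptions. Entries are the exact probability of concluding non-inferiority with 300 per arm and placebo at 1%.

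| Assumed reading of the tafenoquine arm | Rate as read | Wald | Miettinen-Nurminen |
|---|---|---|---|
| True rate 1%, no error | 1.00% | 85% | 72% |
| True rate 1%, 1 extra false call expected | 1.33% | 70% | 54% |
| True rate 1%, 3 extra false calls expected | 2.00% | 37% | 25% |
| True rate 3.5%, none missed | 3.50% | 4.1% | 2.1% |
| True rate 3.5%, 10% missed | 3.15% | 7.3% | 3.9% |
| True rate 3.5%, 20% missed | 2.80% | 12.6% | 7.2% |
| True rate 3.5%, 30% missed | 2.45% | 20.8% | 12.7% |

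In the first three rows a high value is wanted (power). In the last four the true difference equals the margin, so the value is the false non-inferiority rate.

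**4. Strength of the cue.** In the Study 033 subgroup, 69/74 = 93.2% on tafenoquine had deposits (Section 2.1.1.1). In placebo-controlled Study 057, new deposits appeared in 21.4% on tafenoquine and 12.5% on placebo. At 1:1 allocation a new deposit would then point to tafenoquine with probability 0.214 / (0.214 + 0.125) = 63%.

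**5. Which components are exposed.**

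- Central subfield thickness, macular volume and parafoveal thickness come from automated segmentation (Appendix 1) with numeric cut-offs.
- qFAF is labelled a manual reading in Table 5 but has a 12% cut-off on ring averages (Appendix 2).
- Ellipsoid or interdigitating zone disruption is a manual judgement with no numeric threshold. It is the one clearly subjective component.

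Section 12.2.3.1 counts a SOSE if any one component is positive in either eye at any time during treatment, so that one component is enough.

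**The case against.** The documents lean towards the reading centre. Section 9.2.6 ties the site reading to initial reporting, while Sections 9.2.6 and 11.3 send the centre's data to the study database. Section 12 defers detail to a separate SAP, which could name the source. This stands as a reason to expect that the centre was intended. It does not remove the footnote, which assigns the evaluations to the site in the very table that defines the endpoint.

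A reader might infer that the primary endpoint is read unblinded. The documents do not support that.

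- No passage says that the person who grades deposits also reads the scans, and Section 7.6 declares all research staff blinded. What can be said is that the roles are not separated. Section 8.3 allows the ophthalmic assessments to be moved to a second visit, but does not separate slit lamp from imaging.
- The cue is partial. The 93.2% comes from one subgroup, and Study 057 shows deposits on placebo as well.
- The Study 033 precedent concerned fundoscopy without baseline retinal photographs, not stored images compared with baseline.

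A reader might also take both manual rows of Table 5 as subjective. The qFAF row has a numeric criterion, so that goes too far.

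Finally, the power and error figures could be read as forecasts. They are not: the misreading rates are assumed, and the starting value of 85% or 72% depends on an interval that the protocol does not name.

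**Conclusion.** The contradiction is certain and lies in the current text: Table 5 footnote a, the text of Section 12.2.3.1 and Section 9.2.6 do not agree on who reads the primary endpoint, and no rule settles it. It must be resolved before unblinding.

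The risk of bias is conditional. It arises if the footnote governs and if the local reader knows of the deposits, which is a reasonable inference but is not stated. It acts mainly through ellipsoid or interdigitating zone disruption.

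The size of any bias cannot be estimated from the documents. What can be said is that at 3 placebo events the result turns between 4 and 5 tafenoquine events. Small assumed reading errors therefore matter in both directions: power falls from 85% to 70% (Wald) or 72% to 54% (Miettinen-Nurminen) with one extra expected false call, and false non-inferiority rises from 4.1% to 20.8% or from 2.1% to 12.7% if 30% of true tafenoquine events are missed at 3.5% against 1%.

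**What to change.** Before unblinding, replace footnote a of Table 5 with:

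> 'The primary endpoint is derived solely from the Fundus Photograph Reading Center grading of SD-OCT and qFAF, by graders masked to treatment, to the site evaluation, and to slit-lamp findings and corneal images. Site readings are used for real-time AE/SOSE safety reporting and in a sensitivity analysis.'

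The masking clause is needed because Section 9.2.6 describes the centre as masked only in that it does not receive the site's evaluation, and the centre is also sent colour photographs.

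Amend Section 9.2.6 to say that the site PI's review of discordant readings cannot change the reading-centre value. Add a table of site-centre agreement by arm.

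Cost: a protocol amendment, which may count as substantial under Section 14.2.2 and so need ethics approval. No new reading work is required for the primary analysis, because the centre already grades these scans and transfers data monthly. Sample size and power are unchanged. The downside is that the analysed SOSE may differ from the site's real-time safety call; the sensitivity analysis and the agreement table will show where.
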